14.2 EFFICACY DATA

N/A

Careseng 1370 for Healthy Volunteers

14.3 SAFETY DATA

Visit 11 is final visit or early withdrawal visit.

Safety data below except for visit 8 and visit 9 not in its visit window will be shifted to corresponding scheduled visit for analysis as in table below. If there is any data shifting, visit name will be presented as 'Adjusted Visit' for the visits reallocated to its original scheduled visit or the next visit after preceding scheduled visit.

Adjusted Visit	Laboratory Assessment†	Physical Examination	Body Weight	Vital Signs	12-Lead Electrocardiogram
Baseline	N Baseline is Visit 1 (Screening), no need to present statistics for Baseline additionally	N.	Y Baseline is Day 1, or alternatively as Visit 1 if Day 1 data are not available.	Y Baseline is Day 1 Pre-dose, or alternatively as Visit 1 if Day 1 Pre-dose data are not available.	Y Baseline is Day 1 Predose, or alternatively as Visit 1 if Day 1 Predose data are not available.
• Visit 1	Y	Y	Y	Y	Y
• Visit 2 (Day 1)	Y (8 hours post-first dose)	Y (Pre-dose), (8 hours post- first dose)	Y	Y (Pre-dose), (1 hour post-first dose), (4 hours post-first dose), (8 hours post-first dose)	Y (Pre-dose), (1 hour post-first dose), (4 hours post-first dose), (8 hours post-first dose), (12 hours post-first dose)
• Visit 3 (Day 2)	Y	Y	Y	Y	Y (Pre-dose), (1 hour post-first dosing post-first dosing)
• Visit 4 (Day 3)	Y	Y	Y	Y	Y (Pre-dose), (1 hour post-first dosing)
• Visit 5 (Day 4)	Y	Y	Y	Y	Y (Pre-dose), (1 hour post-first dosing)
• Visit 6 (Day 5)	Y (Pre-dose), (4 hours post dosing)	Y (Pre-dose), (4 hours post dosing)	Y	Y (Pre-dose), (4 hours post dosing)	Y (Pre-dose), (1 hour post-first dose), (4 hours post-first dose), (8 hours post-first dose), (12 hours post-first dose)
• Visit 7 (Day 6)	Y	Y	Y	Y	Y
• Visit 8 (Day 7)	N	N	N	N	N
• Visit 9 (Day 8)	N	N	N	N	N
• Visit 10 (Day 12)	Y	Y	Y	Y	Y
• Visit 11 (Day 22)	Y	Y	Y	Y	Y

Y denotes that the Visit is performed in the corresponding tables.

N denotes that the Visit is not performed in the corresponding tables.

[†] Visit 1, 3, 7, 11 only for immunology

Careseng 1370 for Healthy Volunteers

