#### 1.3 **Potential Risks and Benefits**

There will be no potential benefits for healthy volunteers to participate in this study.

Potential risks of Careseng 1370 are based on the toxicology findings in Sprague-Dawley (SD) rats. Possible influence on coagulation prolonged prothrombin time (PT) and activated partial thromboplastin time (APTT) was noted in both sexes of rats receiving mid- (1,350 mg/kg/day) and high-dose (2,700 mg/kg/day) for 13 weeks. But the prolonged PT and APTT were not seen at the end of recovery period in 2,700 mg/kg recovery animals. It was also noted that the mean body weights of mid- and high-dose male rats were 9.3% and 13.8% lower than that of the controls, respectively. Final mean body weight of high-dose recovery male rats was 11.8% lower than that of the controls. Final mean body weight gains of mid- and high-dose male rats were 15.7% and 23.2% lower than that of the controls. Final mean body weight gains of high-dose recovery males was 19.2% lower than that of the controls. Therefore, body weight loss and bleeding prolonged are possible risks that subjects in this study may experience.

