#### 7. STUDY SCHEDULE

In traditional 3+3 paradigm settings, eligible volunteers will be assigned to one of the candidate dose cohorts. The starting dose of the dose escalation scheme begins from

level A.

The schedule of assessment is tabulated in front of the protocol main text. The assessments or procedures to be performed at each study visit are listed below. The results of protocol specific assessments and procedures will be recorded in the source documents for all study volunteers and on the appropriate page of the eCRF. Unscheduled visit will be arranged when investigator considers necessary. Healthy volunteers should come fasted for all scheduled visits except visit 8, and 9. The definition of "pre-dose" means the timing prior to the 1st dose of that day (level A-D), or the timing for examinations scheduled on that day (2nd and 4th days of level D). The definition of "post-dose" means the timing after the 1st dose on Day 5. The duration of dosing time between breakfast and lunch from Day 2 to Day 5 should be as close to those for Day 1. Volunteers should take Careseng 1370 for breakfast on that day. Similarly, time points for pre-dose PK blood sampling on Day 2 to Day 5 should be as close as that on Day 1.

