- Maximum Tolerated Dose (MTD)-Evaluable Population:
 - 1. A subset of ITT population
 - 2. Experiences DLT OR with at least 80% of study drug compliance and has exposed to Careseng 1370 for at least 4 days

(4) For Visit Name (in Tables and Figures) and Visit Code (in Subject Data Listing):

Visit No.	Visit Description	Visit Day	Visit Name	Visit Code
1	Visit 1 Screening Visit	-14 ∼ -1	Visit 1 (Screening)	V01
2	Visit 2 Hospitalization: Day -1 to Day 1	1	Visit 2 (Day 1)	V02D01
3	Visit 3 Discharge: Day 2	2	Visit 3 (Day 2)	V03D02
4	Visit 4: Day 3	3	Visit 4 (Day 3)	V04D03
5	Visit 5: Day 4	4	Visit 5 (Day 4)	V05D04
6	Visit 6 Hospitalization: Day 4 to Day 5	5	Visit 6 (Day 5)	V06D05
7	Visit 7 Discharge: Day 6 (24±2 hrs post-last dose)	6	Visit 7 (Day 6)	V07D06
8	Visit 8 Follow-up Visit: Day 7 (48±2 hrs post-last dose)	7	Visit 8 (Day 7)	V08D07
9	Visit 9 Follow-up Visit: Day 8 (72±2 hrs post-last dose)	8	Visit 9 (Day 8)	V09D08
10	Visit 10 Follow-up Visit: Day 12±2	10 ~ 14	Visit 10 (Day 12)	V10D12
11	Visit 11 Final Visit (Day 22±2, within 3 days after withdrawal)	22	Visit 11 (Day 22)	V11D22
-	Unscheduled Visit	-	-	V□□.□

(5) Full term for 'Protocol Deviation Code':

Code	Full Term
<to added="" be="" data="" final="" in="" real="" tabulation="" upon=""></to>	

(6) For clinical relevance

CS: abnormal and clinically significant LLN: lower limit of normal range NCS: abnormal but not clinically significant ULN: upper limit of normal range

(7) For Transition of Clinical Relevance

Relieved CS (Medical History or Adverse Event) at baseline to Normal / NCS at

visit.

Unchanged Including Normal at baseline to NCS at visit, NCS at baseline to Normal

at visit.

Worsened (Medical History) Normal / NCS at baseline to CS (Medical History) at visit

Worsened (Adverse Event) Normal / NCS / CS (Medical History) at baseline to CS (Adverse Event)

at visit

Version 1.0, 08-SEP-2022 Confidential
Protocol No.: Careseng 1370-01 Page 6 of 20 A2 Healthcare Taiwan Co.

Careseng 1370 for Healthy Volunteers

(8) Abbreviations of statistics

N: number of non-missing values Missing: number of missing values

Mean: mean of values

SD: standard deviation of values Q1: 25% quartile of values Q3: 75% quartile of values

Median: median of values

IQR: inter-quartile-range (IQR=Q3-Q1)

Min: minimum of values Max: maximum of values CI: confidence interval

Version 1.0, 08-SEP-2022 C Protocol No.: Careseng 1370-01 P

Careseng 1370 for Healthy Volunteers

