14.3.5 Laboratory Examination – Immunology

- 14.3.5.1 Immunology CD3 <Unit>
- 14.3.5.2 Immunology CD4 <Unit>
- 14.3.5.3 Immunology CD8 < Unit>
- 14.3.5.4 **Immunology CD16 < Unit >**
- 14.3.5.5 **Immunology CD19 < Unit >**

Version 1.0, 08-SEP-2022 Protocol No.: Careseng 1370-01

Careseng 1370 for Healthy Volunteers

<For continuous Laboratory Examination >

Population: Intent-to-Treat Population

opulation: Intent-to-Treat I opulation	
Characteristics	Dose Level
. (Adjusted) Visits, see visit table below 14.3	
n (Missing)	XXX (XXX)
Mean (SD)	XXX (XXX)
Median (IQR)	XXX (XXX)
Q1~Q3	XXX~XXX
Min~Max	XXX~XXX
n (Missing)	XXX (XXX)
Normal	XXX (XX.X%)
NCS	XXX (XX.X%)
CS (Medical History)	XXX (XX.X%)
CS (Adverse Event)	XXX (XX.X%)
. (Adjusted) Visits - Baseline, see visit table below	
n (Missing)	XXX (XXX)
Mean (SD)	XXX (XXX)
Median (IQR)	XXX (XXX)
Q1~Q3	XXX~XXX
Min~Max	XXX~XXX
95% CI (WI)	XXX~XXXwt
. Baseline to (Adjusted) Visits, see visit table belo	pw 14.3
n (Missing)	XXX (XXX)
Relieved	XXX (XX.X%)
Unchanged	XXX (XX.X%)
Worsened (Medical History)	XXX (XX.X%)
Worsened (Adverse Event)	XXX (XX.X%)

- For CI (WI, within group), t denotes by using one sample t-test, w denotes CI of median (determined by Shapiro-Wilk normality test)
- Refer to [Instructions and Abbreviations] of title pages for Transition of Clinical Relevance

Programmer's Notes:

Present 'Baseline' as Visit 1 (Screening).

Careseng 1370 for Healthy Volunteers

For categorical urinalysis data>Population: Intent-to-Treat Population

Population: Intent-to-Treat Population		
Characteristics	Dose Level	
. (Adjusted) Visits, see visit table below 14.3		
n (Missing)	XXX (XXX)	
<value 1=""></value>	XXX (XX.X%)	
<value 2=""></value>	XXX (XX.X%)	
<value 3=""></value>	XXX (XX.X%)	
n (Missing)	XXX (XXX)	
Normal	XXX (XX.X%)	
NCS	XXX (XX.X%)	
CS (Medical History)	XXX (XX.X%)	
CS (Adverse Event)	XXX (XX.X%)	
Baseline to (Adjusted) Visits, see visit table below	14.3	
n (Missing)	XXX (XXX)	
<value 1=""></value>	XXX (XX.X%)	
<value 2=""></value>	XXX (XX.X%)	
<value 3=""></value>	XXX (XX.X%)	
Baseline to (Adjusted) Visits, see visit table below	14.3	
n (Missing)	XXX (XXX)	
Relieved	XXX (XX.X%)	
Unchanged	XXX (XX.X%)	
Worsened (Medical History)	XXX (XX.X%)	
Worsened (Adverse Event)	XXX (XX.X%)	
,	,	

Refer to [Instructions and Abbreviations] of title pages for Transition of Clinical Relevance

Programmer's Notes:

Present 'Baseline' as Visit 1 (Screening).

Careseng 1370 for Healthy Volunteers

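### The SAP laboratory tables give unscheduled INR and APTT results no stated place, and none counts volunteers with any post-dose prolongation

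*SAP*

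**What the plan says.** Protocol section 1.3 reports prolonged PT and APTT in mid- and high-dose rats of both sexes. It concludes that body weight loss and "bleeding prolonged are possible risks that subjects in this study may experience". INR and APTT are measured within the hematology panel (Protocol 6.5).

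Protocol section 7 adds that "Unscheduled visit will be arranged when investigator considers necessary", with the tests done at such a visit left to the investigator apart from recording adverse events and concomitant medication.

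In the SAP, the visit table in 14.3 has rows for Baseline and Visits 1 to 11 only, and explains that "Y denotes that the Visit is performed in the corresponding tables". Off-window data are handled by this rule: "Safety data below except for visit 8 and visit 9 not in its visit window will be shifted to corresponding scheduled visit for analysis". An adjusted-visit label is used "for the visits reallocated to its original scheduled visit or the next visit after preceding scheduled visit". The change and transition blocks of the laboratory layout (shown after 14.3.5) take their rows from that table, as in "Baseline to (Adjusted) Visits, see visit table below".

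The visit key in SAP section 4, item (4), covers both table names and listing codes. Its unscheduled-visit line has a dash for visit day, a dash for visit name, and a code for listings only. Item (7) of the same section places a change from normal to NCS (abnormal but not clinically significant) under Unchanged.

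**The concern.** Unscheduled tests are ordered when the investigator sees a reason, so their results can be informative about a suspected harm. If they have no row, an INR or APTT that is raised but not judged clinically significant reaches no summary table. Under Protocol 8.1 a laboratory abnormality becomes an AE only when the investigator judges it clinically significant, so the AE tables do not catch it either.

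Scheduled results have a related gap. Each is summarised at its own visit, and nothing adds up over visits within a volunteer. A reader who wants to know how many of the volunteers at a dose level ever had a prolonged INR or APTT after dosing cannot find that number in any planned table. With 3 to 6 evaluable volunteers per level, one person is 1/3 = 33.3% or 1/6 = 16.7% of the cohort, so the count matters to how the level is described.

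**Working it through.** The plan states no figure for this point. The check sets the table rows against the protocol schedule.

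**1. Post-dose laboratory rows (SAP 14.3 visit table).** Day 1 at 8 h, Day 2, Day 3, Day 4, Day 5 pre-dose, Day 5 at 4 h, Day 6, Day 12 and Day 22: 9 scheduled rows. Unscheduled rows: 0. Any-time or worst-value rows: 0.

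**2. Does the shifting rule bring unscheduled results in?** The rule concerns data outside a visit window, and an unscheduled visit has none. Visit Adjustment (16.2.1.4) and Unscheduled Visit Dates (16.2.1.5) are separate listings, which suggests that the SAP treats them as different things. If shifting were intended, nothing says which value is used when the scheduled slot is already filled. Listing-only handling is therefore the most plausible reading, but it is an inference.

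**3. Days without scheduled laboratory tests.** Visits 8 and 9 (Days 7 and 8) are marked N. Visit 10 falls on Days 10 to 14. For a volunteer still on schedule, any INR or APTT on Days 7 to 9 is therefore unscheduled, as is one on Day 10 unless Visit 10 is held then. That is 3 to 4 days of the Day 1 to Day 10 DLT period.

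**4. What the transition rows can show.**

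| Change in APTT from baseline | Transition category | Reaches the AE tables? |
|---|---|---|
| Normal to NCS | Unchanged | No |
| Normal or NCS to CS (Adverse Event) | Worsened (Adverse Event) | Yes |

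A prolongation that is not clinically significant is invisible in the transition rows, whether scheduled or unscheduled. At scheduled visits it does enter that visit's NCS count and the minimum-to-maximum range. However, NCS does not distinguish high from low values, and the counts cannot be added over visits without double counting volunteers.

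**5. Behaviour of an ever-above-ULN count.** Assume that each of the 9 scheduled tests in an unaffected volunteer exceeds ULN with probability p, independently. The documents give no p, so a range is shown.

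P(at least one) = 1 − (1 − p)^9

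| p per test | P(at least one in 9) | Expected in a cohort of 6 |
|---|---|---|
| 1% | 1 − 0.99^9 = 0.087 (9%) | 0.5 |
| 2.5% | 1 − 0.975^9 = 0.204 (20%) | 1.2 |
| 5% | 1 − 0.95^9 = 0.370 (37%) | 2.2 |

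Independence is a simplification. Positive correlation between repeat tests in one volunteer would generally lower these figures, and unscheduled tests would raise them.

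**The case against.** **The tables deliver what was promised.** The protocol's secondary endpoint is change from baseline to applicable post-dosing visits, and by-visit tables can meet that wording. This stands: the point is a gap in reporting, not a broken commitment.

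**Nothing is hidden.** With at most 6 evaluable volunteers per level and 24 overall, the hematology listing and the listing of unscheduled dates can be read person by person. By-visit NCS counts and ranges also show scheduled excursions. This stands too, so a reader who infers that the tables would show no coagulation shift at all goes too far. Reading listings still leaves each reader to do the count.

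**The primary results are safe.** AE and DLT tables count each volunteer once, whichever visit found the event, and MTD decisions rest on DLTs in evaluable volunteers. A reader might infer that dose decisions are exposed; the documents do not support that.

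**Early withdrawals are covered.** A reader might infer that unscheduled tests are the only laboratory data possible between Day 6 and Visit 10. That is not so. Under Protocol 4.3 and the Final Visit schedule, a volunteer who stops has Final-visit procedures, including laboratory tests, within 3 days where possible, and the SAP tabulates these as Visit 11. The statement holds only for volunteers still on schedule.

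**A worst-value row collects noise.** With no control arm, some volunteers will exceed ULN by chance. This is a real cost and must be shown with the count.

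**Conclusion.** The concern holds as a reporting gap in a descriptive secondary endpoint. The laboratory tables have 9 scheduled post-dose rows, no stated place for unscheduled results and no per-volunteer summary over time. Together with the coding of normal to NCS as Unchanged, this means that no planned table gives the number of volunteers with any post-dose INR or APTT prolongation.

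A reader might infer that the SAP expressly excludes unscheduled results. It does not: it leaves their handling unstated, and listing-only treatment is the likeliest outcome of the layout.

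The size of the loss cannot be estimated, because the documents give no rate of unscheduled coagulation testing. What can be said is that one uncounted volunteer is 16.7% of a cohort of 6 or 33.3% of a cohort of 3, and that only values not reported as AEs are at issue. The gap applies to the other laboratory, vital-sign, weight and EKG summaries as well; coagulation is the priority because the protocol names the risk.

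**What to change.** 1. State in SAP 14.3 that by-visit rows use scheduled (or adjusted) visits only and that unscheduled results enter the summaries in item 2 and the listings.
2. For INR and APTT, add per dose level:
   - the number of volunteers with any post-dose value above ULN, scheduled or unscheduled, split by baseline at or below ULN versus above ULN;
   - the change from baseline to each volunteer's highest post-dose value.
3. If the change row is extended to platelets, hemoglobin or body weight, use the lowest post-dose value and say so.
4. Do not use the existing Relieved/Unchanged/Worsened categories for these rows, since they would code a non-clinically-significant prolongation as Unchanged.
5. Footnote the numbers of scheduled and unscheduled tests behind each count and label the count as descriptive, given the chance excursions shown in the working.

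The cost is a few table rows and one sentence. The data are already collected and listed, the by-visit rows stay as they are, and no dose, schedule or clinical rule changes.

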## Follow-up visits:

- Day 6: post-dose PK blood sampling for 24 hours, discharge from hospitalization
- Day 7: post-dose PK blood sampling for 48 hours
- Day 8: post-dose PK blood sampling for 72 hours
- Day 12 (±2)

*Note: The definition of "post-dose PK blood sampling" means blood collection for PK after the 1st dose on Day 5.* 

Final visit: Day 22 (±2) or within 3 days after withdrawal is confirmed

Volunteers Inclusion A healthy volunteer is eligible for the study if all of the followings		
Criteria	apply:	
	1. Adult aged between 20-40 years old (inclusive)	
	2. Physically and mentally healthy volunteer as confirmed by an interview, medical history, clinical examination, chest X-rays, and electrocardiogram. Volunteer with non-clinically significant signs or symptoms may be eligible at investigator's discretion.	
	3. Body Mass Index (BMI) between 18.5 and 24, inclusive (BMI will be calculated as weight in kilogram [kg]/(height in meters)  [m  ])	
	4. Clinically normal hematology, biochemistry and urinalysis determinations based on investigator's discretion. Volunteer with non-clinically significant signs or symptoms may be eligible at investigator's discretion.	
	5. Volunteer is willing and able to comply with study procedures and sign informed consent prior to initiation of any study-mandated procedures.	
Volunteers Exclusion Criteria	Any volunteer meeting any of the exclusion criteria will be excluded from study participation:	
	1. Volunteer who has a history or evidence of a medical condition that would expose them to a risk of a significant adverse event or interfere with the assessments of safety or pharmacodynamics variables during the course of the trial, including but not limited to hepatic, renal, respiratory, cardiovascular, endocrine, immune, neurological, musculoskeletal or hematological disease as determined by the clinical judgment of the investigator	
	2. Volunteer has received any other investigational agent within 4 weeks prior to the first dose of study drug	
	3. Volunteer has taken or potentially takes any herbal medication/supplements/medicinal food, prescription medication and/or over-the-counter medication within 2 weeks prior to the first	

dose of study drug

- 4. Volunteer has consumed alcohol, caffeine, grapefruit juice, nicotine, phosphorous supplement, calcium supplement, or food rich in calcium within 24 hours prior to the first dose of study drug

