## 4.3 Dose Delay and Discontinuation Rules

Healthy volunteers will discontinue Careseng 1370 if experiencing DLT or intolerable toxicity. If volunteers in level A, B or C happen to miss or delay dosing not owing to DLT or intolerable toxicity, volunteers may continue the next dosing. If volunteers in level D happen to miss or delay dosing not owing to DLT or intolerable toxicity, volunteers should be withdrawn from the study. For level A, B and C, volunteer who misses dosing and fails to reach 80% of study drug compliance should be withdrawn from the study. For level D, volunteer who misses any dosing should be withdrawn from the study.

If possible, volunteers will be assessed using the procedures planned for the Final visit within 3 days after withdrawal is consented or Careseng 1370 is discontinued.

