1.1 Visit Adjustment

Visit 11 is final visit or early withdrawal visit, refer to 14.3 for detail of visit adjustment

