14.1.2 Study Visits, Study Termination, Subject Disposition and Protocol Deviation

Population: Intent-to-Treat Population	
Characteristics	Dose Level
. Study Termination	
n	XXX
Study Completed	XXX (XXX.X%)
Study Not Completed	XXX (XXX.X%)
Withdrew consent	XXX (XXX.X%)
Protocol issue	XXX (XXX.X%)
•••	XXX (XXX.X%)
. Study Duration [days]	
n (Missing)	XXX
Mean (SD)	XXX (XXX)
Median (IQR)	XXX (XXX)
Q1~Q3	XXX~XXX
Min~Max	XXX~XXX
.Population	*****
n NATE E 1 11	XXX
MTD-Evaluable	XXX (XXX.X%)
Non-MTD-Evaluable	XXX (XXX.X%)
<reason 1=""></reason>	XXX (XXX.X%)
<reason 2=""></reason>	XXX (XXX.X%)
	XXX (XXX.X%)
.Protocol Deviation	
n	XXX
Major Protocol Deviation	XXX (XXX.X%)
<protocol 1="" deviation=""></protocol>	XXX (XXX.X%)
<protocol 2="" deviation=""></protocol>	XXX (XXX.X%)
Minor Protocol Deviation	XXX (XXX.X%)
<protocol 1="" deviation=""></protocol>	XXX (XXX.X%)
<protocol 2="" deviation=""></protocol>	XXX (XXX.X%)
. Study Visits Completed, Adjusted Visits Completed	
N	XXX
Visit 1 (Screening)	XXX (XXX.X%)
Visit 2 (Day 1)	XXX (XXX.X%)
Visit 3 (Day 2)	XXX (XXX.X%)
Visit 4 (Day 3) Visit 5 (Day 4)	XXX (XXX.X%) XXX (XXX.X%)
Visit 5 (Day 4) Visit 6 (Day 5)	XXX (XXX.X%) $XXX (XXX.X%)$
Visit 7 (Day 6)	XXX (XXX.X%)
Visit 8 (Day 7)	XXX (XXX.X%)
Visit 9 (Day 8)	XXX (XXX.X%)
Visit 10 (Day 12)	XXX (XXX.X%)
Visit 11 (Day 22)	XXX (XXX.X%)

Study Duration [days] = Date of Termination - Visit 1, or alternatively as the last visit date - Visit 1 Adjusted Visits Completed: Visits except visit 8 and visit 9 not in its visit window are shifted to corresponding scheduled visits

Careseng 1370 for Healthy Volunteers

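### SAP 1.1 and 14.3 name two destinations for early-withdrawal assessments and no rule for choosing, and either one can put off-drug values in an unsuitable by-visit row

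*SAP*

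**What the plan says.** SAP 1.1 reads: "Visit 11 is final visit or early withdrawal visit, refer to 14.3 for detail of visit adjustment". SAP 14.3 then gives the rule: "Safety data below except for visit 8 and visit 9 not in its visit window will be shifted to corresponding scheduled visit for analysis". The adjusted-visit label is to be used "for the visits reallocated to its original scheduled visit or the next visit after preceding scheduled visit". The footnote to table 14.1.2 repeats the rule without adding a destination: "Visits except visit 8 and visit 9 not in its visit window are shifted to corresponding scheduled visits".

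On timing, the protocol's visit list places the final visit at "Day 22 (±2) or within 3 days after withdrawal is confirmed". Protocol 4.3 asks for the same procedures, if possible, "within 3 days after withdrawal is consented or Careseng 1370 is discontinued". The final or withdrawal visit includes laboratory tests with immunology (Protocol 7, Final Visit).

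The footnote to the SAP 14.3 table limits immunology rows: "Visit 1, 3, 7, 11 only for immunology". Visits 8 and 9 have no safety rows at all. The SAP visit table gives single days for Visits 2 to 6 and Days 10 to 14 for Visit 10. For Visit 11 it shows Day 22 in the day column, but puts both the Day 22 window and the three-day withdrawal window in the description.

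**The concern.** One visit code covers two different assessments: a scheduled one about 17 days after the last dose, and an unscheduled one within about 3 days of stopping. The reallocation wording offers two destinations and no criterion. It does not define the original scheduled visit for a withdrawal assessment.

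By-visit changes from baseline in laboratory values, vital signs, weight and EKG are a secondary endpoint (Protocol 2.2.2), summarised by dose level with 95% intervals. Lymphocyte subsets on Days 2, 6 and 22 are exploratory (Protocol 2.2.3). An acute value in the Day 22 row can look like failed recovery. A value taken off drug but placed in a dosing-day row can blur the on-treatment picture. A DLT is both a reason to discontinue (Protocol 4.3) and a withdrawal criterion (Protocol 3.4), so some of the volunteers affected could be the ones of most interest.

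The trial is unblinded. The SAP is dated 8 September 2022 and expects the last subject to leave in March 2022. If that date was met, an unstated choice would be made with the data already in hand.

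**Working it through.** The plan gives no figure to reproduce. The check enumerates where the rule sends a withdrawal assessment.

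**Inputs**
- Visit days (SAP visit table): Visits 2 to 9 are Days 1 to 8; Visit 10 is Day 12 ±2; Visit 11 is Day 22 ±2.
- Withdrawal assessment: up to 3 days after withdrawal or discontinuation (Protocol 4.3).
- Safety rows: none at Visits 8 and 9. Immunology rows: Visits 1, 3, 7 and 11 (SAP 14.3).
- Assumption: withdrawal is confirmed on the day of the last attended visit, and the assessment follows 1, 2 or 3 days later.

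**Cases:** 8 possible last visits (Visits 2 to 9) × 3 lags = 24. These are scenarios, not probabilities.

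**Destination 1, kept in Visit 11.** Error = 22 − actual day.
- Earliest assessment, Day 1 + 1 = Day 2: 22 − 2 = 20 days.
- Latest assessment, Day 8 + 3 = Day 11: 22 − 11 = 11 days.
- The day is wrong in 24 of 24 cases. An immunology row exists in all 24.

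**Destination 2, moved to the next visit with a safety row.** Error = day of that visit − actual day.
- Exact in 5 of 24 cases (last visit 2 to 6, lag 1 day); off in 19, by −2 to +5 days.
- Allowing Visit 10's ±2 days, 19 − 3 = 16 of 24 are off.
- The target is Visit 3, 4, 5 or 6 when the last visit was 2, 3, 4 or 5: 4 × 3 = 12 of 24. For levels A to C these are all dosing days; for level D only Visits 4 and 6 are.
- No immunology row: Visits 4, 5 and 6 take 3 cases each and Visit 10 takes 9, so 9 + 9 = 18 of 24.

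**Sensitivity.** With lags of 0 to 3 days (32 cases), destination 1 is off by 11 to 21 days. Destination 2 is on the wrong day in 27 of 32 and has no immunology row in 24 of 32. If Visits 8 and 9 are not skipped (24 cases), destination 2 is on the wrong day in 17 and has no immunology row in 18.

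**One case.** A volunteer stops after Visit 4 (Day 3) and is assessed on Day 6, about 72 hours after the last dose. Destination 1 prints the values as Day 22 (22 − 6 = 16 days off). Destination 2 prints them as Visit 5, Day 4 (4 − 6 = −2 days), with no immunology row.

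**Weight in a row.** The by-visit tables use the ITT population, so replaced volunteers stay in.
- A non-evaluable volunteer beside 3 evaluable ones: 1/4 = 25%.
- Beside 6 evaluable ones: 1/7 = 14%.
- A single DLT stop: one DLT in three expands the cohort to six, so 1/6 = 17%.

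**The case against.** **The withdrawal visit may already be in window.** The SAP visit table writes the three-day withdrawal window into Visit 11. An on-time withdrawal visit then needs no shift, its immunology row exists, and 14.3 states openly that "Visit 11 is final visit or early withdrawal visit". This reading is available, though the pointer from 1.1 to the adjustment rule leaves it arguable. It removes the dosing-day and missing-row problems but leaves values from the first days in a row labelled Day 22. With nothing shifted, neither the adjusted-visit label nor the adjustment listing would flag them.

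**The corresponding visit might be the one nearest the actual day.** In the Day 6 example that is Visit 7, which has every row, including immunology. The SAP does not state this reading. It would also place a volunteer about 72 hours off drug in a row that the SAP describes as 24 ±2 hours after the last dose.

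**The consequences are limited.** This stands. AE, SAE and DLT tables are not by visit. The MTD rests on DLTs in evaluable volunteers. Clinically significant laboratory abnormalities can be recorded as AEs. Listings give visit dates, adjustments, treatment dates and every result by subject, so in cohorts this small a misplaced value can be traced. A listing does not correct a summary table, however.

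**A separate row is not the only remedy.** Mapping by actual day with windows for every visit would also give a defined rule.

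**Conclusion.** The SAP lacks a usable rule for early-withdrawal assessments, and each destination it names can give a misleading row. This should be corrected before the tables are produced. The size is roughly 14% to 25% of a dose-level row per affected volunteer, in descriptive tables only. It rests on the timing assumption above and on at least one early withdrawal with an assessment; the documents do not say how many there were.

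A reader might infer more, and the documents do not support it:
- That withdrawal data are certain to appear on the wrong day and also to lose their immunology row. These faults belong to different destinations: Visit 11 keeps the immunology row, and the next visit is sometimes the right day.
- That one volunteer stopping for a DLT is a third of a row. A single DLT in three expands the cohort to six; a cohort that halts at three has at least two DLTs.
- That those affected are mainly toxicity stops, or number about five (29 recruited less 24 evaluable). Withdrawal also covers consent, missed doses and missed appointments, and non-evaluable is not the same as withdrawn with an assessment.
- That the primary endpoint or the MTD is affected. Neither depends on visit rows.

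**What to change.** In SAP 1.1 and 14.3:
- State that early-withdrawal assessments are not shifted to a scheduled visit.
- Add one early-withdrawal row to each by-visit safety table and each immunology table, showing actual study day and days since last dose.
- Limit the Visit 11 (Day 22) row to assessments on Day 22 ±2, and make the visit table agree.
- Keep the shift rule only for mistimed attendance at a volunteer's own scheduled visit.

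The cost is SAP wording and one extra row per table, which will often be sparse or empty. No new data are needed, and no clinical rule or visit schedule changes.
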